6.2 Study Assessments

6.2.1 Laboratory Assessments

Blood samples for clinical laboratory and PK assessments will be collected throughout the Study as detailed in Appendices A and C. A list of laboratory and PK analytes is contained in Appendix B.

6.2.2 Safety

Subjects with a suspected bleeding event will undergo additional testing if deemed appropriate by the treating physician and an (S)AE case report form will be completed. In addition, if

bleeding is considered significant, hemoglobin (Hb), hematocrit (Hct), aPTT, PT, INR, and platelet count are to be obtained, and approximately 2 mL of K2EDTA anticoagulated blood will be collected. The resulting plasma must be stored allowing for a centralized assessment of ISIS 416858 concentrations.

If the platelet value or liver enzyme tests are uninterpretable (e.g., due to clumping, hemolysis or quantity not sufficient) or missing, a repeat blood specimen must be re-drawn as soon as possible (ideally within 7 days).

Subjects that withdraw from the study due to a change in dialysis modality or to undergo renal transplantation should notify the Sponsor Medical Monitor (or designee) and conduct the early termination procedures identified in [Appendices A](#) and [C](#) prior to the change or the surgery as appropriate. Whenever possible, a coagulation panel and PK blood sample should be collected prior to the initiation of renal transplant surgery. Additionally, at approximately 48 hours post-transplant, additional blood samples should be collected for Coagulation Panel ([Appendix B](#)) and ISIS 416858 plasma concentration (Appendix C). Any clinically-significant bleeding such as CRNMB and MB should be recorded and reported to the Sponsor Medical Monitor (or designee).

6.2.3 Clotting Assessments

Clotting assessments of the dialysis filter will be conducted throughout the Study as indicated in Appendix A. The clotting assessment will consist of a semi-quantitative scale by descriptive category (See [Section 10.6.4](#)) and will be performed by trained personnel.

6.3 Restriction on the Lifestyle of Subjects

6.3.1 Contraception Requirements

All male subjects and women of childbearing potential must refrain from sperm/egg donation and either be abstinent or practice highly effective contraception from the time of signing the informed consent form until at least 12 weeks after their last dose of study treatment.

Male subjects engaged in sexual relations with a female of child-bearing potential must also encourage their female partner to use highly effective contraception from the time of signing the informed consent until 12 weeks after the subject's last dose of study treatment.

For the purposes of this study, women of childbearing potential are defined as any female who has experienced menarche, and who does not meet one of the following conditions:

- Postmenopausal: 12 months of spontaneous amenorrhea in females > 55 years of age or, in females ≤ 55 years, 12 months of spontaneous amenorrhea without an alternative medical cause and FSH levels in the postmenopausal range for the laboratory involved
- 6 weeks after surgical bilateral oophorectomy with or without hysterectomy
- Post hysterectomy

For the purposes of the study, effective contraception is defined as follows:

For male subjects:

- Effective male contraception includes a vasectomy with negative semen analysis at Follow-up, or the use of condoms together with spennicidal foam/gel/film/cream/supposito1y
- Male subjects with pa1tners that are pregnant must use condoms as contraception to ensure that the fetus is not exposed to the Study Drng

For female subjects and female pa1tners of male subjects:

- Using 1 or more of the following acceptable methods of contraception: surgical sterilization (e.g., bilateral tubal ligation), hormonal contraception, intrauterine contraception/device, or any 2 barrier methods (a combination of male or female condom* with diaphragm, sponge, or ce1vical cap) together with spermicidal foam/gel/film/cream/suppositmy

tNote: Abstinence is only acceptable as true abstinence, i.e., when this is in line with the preferred and usual lifestyle of the patient. Periodic abstinence (e.g., calendar, ovulation, symptothermal, post-ovulation methods), declaration of abstinence for the duration of a trial and withdrawal are not acceptable methods of contraception.

***Note:** A female condom and a male condom should not be used together as friction between the two can result in either or both products failing.

7. STUDY DRUG

7.1 Study Drug Description

Study Drug (ISIS 416858 or placebo) characteristics are listed in Table 2.

The Study Drug (ISIS 416858 or placebo) is contained in 2 mL stoppered glass vials. The Study Drng (ISIS 416858 or placebo) and its storage and preparation instrnctions will be provided by the Sponsor or designee. The Study Drug (ISIS 416858 or placebo) must be stored securely at 2-8 °Celsius and be protected from light.

Table 2 Study Drug Charactel'istics

Study Drug	ISIS 416858	Placebo
Strength	200 mg/ml	Not Applicable
Volume	1 ml solution per vial	1 ml solution per vial
Route of Administration	Subcutaneous (SC)	Subcutaneous (SC)

7.2 Packaging and Labeling

The Sponsor will provide the Investigator with packaged Study Drng (ISIS 416858 or placebo) labeled in accordance with specific country regulatory requirements.

7.3 Study Drug Accountability

The study staff is required to document the receipt, dispensing, and return of Study Drng (ISIS 416858 or placebo) supplies provided by the Sponsor. The Study Center must return all used and unused Study Drng (ISIS 416858 or placebo) to the Sponsor or designee.

8. TREATMENT OF SUBJECTS

8.1 Study Drug Administration

Study Drng (ISIS 416858 or placebo) will be administered SC by trained personnel at the Study Center. Volumes to be administered are shown in Table 3. All doses of Study Drng will be administered after the completion of the hemodialysis treatment which can be while blood is returning to the patient but must be within 2 hours (preferably within 15 minutes of the conclusion of dialysis). Vials are for single use only. Please refer to the Study Drng Manual provided by the Sponsor (or designee) for more detailed instructions for Study Drng (ISIS 416858 or placebo) preparation and administration.

Table 3 Study Drug Dosing Information

Cohort	Volume to Administer	Number of Injections	Total Dose*
Cohort A (200 mg ISIS 416858 or placebo)	1.0 ml	1 of 1.0 ml	5200 mg ISIS 416858 or placebo
Cohort B (250 mg ISIS 416858 or placebo)	1.25 ml	1 of 0.75 ml and 1 of 0.5 ml	6500 mg ISIS 416858 or placebo
Cohort C (300 mg ISIS 416858 or placebo)	1.5 ml	2 of 0.75 ml	7800 mg ISIS 416858 or placebo

* Total dose of ISIS 416858 based on completed treatments for each cohort

8.2 Other Protocol-Required Drugs

A 0.9% sterile saline will be used for the SC tolerability injections performed during screening. At screening period Study Day S-14 (\pm 3) and S-7 (\pm 3), subjects should receive 2 noncontiguous SC injections of 0.75 mL saline to be administered following procedures for Study Drng as described in Section 8.1.

8.3 Other Protocol-Required Treatment Procedures

Subjects are required to be receiving in center hemodialysis at least 3 times a week for a minimum of 9 hours per week while receiving Study Drng during the treatment period. Subjects no longer receiving the required in center hemodialysis should continue in the study with the regularly scheduled assessments, but will no longer receive Study Drng.

8.4 Treatment Precautions

Please refer also to the 'Guidance for Investigator' section of the Investigator's Brochure.

8.5 Safety Monitoring Rules

Please refer also to the 'Guidance for Investigator' section of the Investigator's Brochure.

Baseline for the routine clinical assessments of chemistry and hematology, PD markers, assessment of clotting, PK assessments, vital signs and ECG for the study will be the last non-missing value prior to the first administration of Study Drug and prior to dialysis on Day 1 ([Appendix A](#)). If Day 1 values are not available, screening values will be used.

For baseline Urea Reduction Ratio determination, the BUN blood collection prior to dialysis as well as the post-dialysis sample on Day 1 will be used.

In addition to the standard monitoring of clinical safety parameters, the following guidelines are provided for the monitoring of selected parameters chosen based on preclinical and clinical observations.

Confirmation Guidance: At any time during the study (Treatment or Post-Treatment Evaluation Periods), any clinical laboratory results meeting the safety monitoring criteria presented below **must be confirmed** by performing measurements (ideally in the same laboratory that performed the initial measurement) on new specimens. All new specimen collections should take place as soon as possible (ideally within 7 days of the initial collection). For stopping rules, if the initial laboratory result is observed during the Treatment Period, the results from the retest **must be available** prior to administering the next dose of Study Drug (ISIS 416858 or placebo).

Re-dosing Guidance: Subjects with initial laboratory test values that reach a stopping rule must not be re-dosed until the re-test results are available. In general, subjects who do not meet the stopping rules based upon retest may continue dosing. However, the Investigator and the Sponsor Medical Monitor (or designee) should confer as to whether additional close monitoring of the subject is appropriate. If any of the stopping criteria described in [Sections 8.6.1, 8.6.2, or 8.6.3](#) are met, the subject will be permanently discontinued from further treatment with Study Drug (ISIS 416858 or placebo), evaluated fully as outlined below and in consultation with the Sponsor Medical Monitor or designee, and will be followed up in accordance with [Section 8.8](#) of the protocol.

8.5.1 Safety Monitoring Rules for Liver Chemistry Tests

The following rules are adapted from the draft guidance for industry, "Drug-Induced Liver Injury: Premarketing Clinical Evaluation," issued by the U.S. Department of Health and Human Services, Food and Drug Administration, July 2009. For a definition of Baseline, please refer to guidance in Section 8.5 above.

In the event of an alanine aminotransferase (ALT) or aspartate aminotransferase (AST) measurement that is $> 3 \times$ ULN, or $3 \times$ baseline value if the baseline value was $>$ ULN at any time during the study (treatment and post-treatment evaluation periods), the initial measurement(s) should be confirmed as described above. Additionally, confirmatory measurements should also be performed if ALT or AST levels increase to $5 \times$ ULN.

Frequency of Repeat Measurements:

If the patient has confirmed post-baseline ALT or AST levels $> 3 \times \text{ULN}$, or $2 \times \text{baseline value}$, if the baseline value was $> \text{ULN}$ at any time during the study (treatment or post-treatment evaluation periods) that are continuing to rise, they should have their liver chemistry tests (ALT, AST, INR and total bilirubin) retested at least once-weekly until ALT and AST levels become $\leq 1.2 \times \text{ULN}$ or $\leq 1.2 \times \text{baseline}$ if the baseline value was $> \text{ULN}$.

Further Investigation into Liver Chemistry Elevations:

For patients with confirmed ALT or AST levels $> 3 \times \text{ULN}$ (or the greater of $2 \times \text{baseline value}$ or $3 \times \text{ULN}$ if baseline value was $> \text{ULN}$), the following evaluations should be performed:

1. Obtain a more detailed history of symptoms and prior and concurrent diseases
2. Obtain history for concomitant drug use (including nonprescription medications, herbal and dietary supplement preparations), alcohol use, recreational drug use, and special diets
3. Obtain a history for exposure to environmental chemical agents and travel
4. Serology for viral hepatitis (hepatitis A virus [HAV] IgM, hepatitis B surface antigen [HBsAg], hepatitis C virus [HCV] antibody, cytomegalovirus [CMV] IgM, and EBV antibody panel)
5. Serology for autoimmune hepatitis (e.g., antinuclear antibody [ANA])

Additional liver evaluations, including gastroenterology/hepatology consultations, hepatic computed tomography (CT) or magnetic resonance imaging (MRI) scans, may be performed at the discretion of the Investigator, in consultation with the Sponsor Medical Monitor (or designee). Repetition of the above evaluations should be considered if a patient's ALT and/or AST levels reach $\geq 5 \times \text{ULN}$.

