5.2 Exclusion Criteria

1. Subjects with a history of a major medical event (e.g., previous acute coronary syndrome, stroke or transient ischemic attack, or systemic thromboembolic event) within 3 months of screening, major surgery within 3 months of screening, or new major physical examination finding (not accounted for by past medical history), except for documented AF.

2. Active bleeding (as judged clinically-significant by the Investigator) within the past 3 months from screening or documented bleeding diathesis (excluding uremia), coagulopathy, or recent history of prolonged compression time at arteriovenous fistula.
3. Screening laboratory results as follows:
 - Platelet count < 150,000 cells/mm³
 - < 180,000 cells/mm³ for platelet function/activation subgroup
 - INR > 1.4
 - aPTT > upper limit of normal (ULN)
 - FXI activity < 0.3 U/mL
 - ALT or AST > 2xULN
 - Total bilirubin > ULN
4. Subject is not willing to have weekly SC injections over the study period as assessed during screening.
5. Active infection requiring systemic antiviral or antimicrobial therapy that will not be completed prior to Study Day 1 (first dose) or IV antibiotic use at the time of screening.
6. Unwillingness to comply with study procedures, including follow-up, as specified by this protocol, or unwillingness to cooperate fully with the Investigator.
7. Known history of or positive test at Screening for human immunodeficiency virus (HIV), hepatitis C or chronic hepatitis B.
8. Malignancy within 5 years, except for basal or squamous cell carcinoma of the skin or carcinoma *in situ* of the cervix that has been successfully treated. Subjects with a history of other malignancies that have been treated with curative intent and which have no recurrence within 5 years may also be eligible if approved by the Sponsor Medical Monitor (or designee).
9. Treatment with another investigational drug, biological agent, or device within one month of screening, or 5 half-lives of investigational agent, whichever is longer.
10. Any history of previous treatment with an oligonucleotide (including siRNA). Subjects that have previously received only a single-dose of an ISIS-oligonucleotide as part of a clinical study may be included as long as a duration 2:4 months has elapsed since dosing.
11. Attending nephrologist answers "no" to the question, "Would you be surprised if this patient died in the next year?"
12. Within 6 months prior to screening,

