8.6.1 Stopping Rules for Liver Chemistry Elevations

In the event of confirmed laboratory results meeting the following criteria, **and the event is without an alternative explanation as discussed with the Sponsor Medical Monitor (or designee)**, dosing of a patient with Study Drug (ISIS 416858 or placebo) will be stopped permanently; values that are not confirmed due to failure to retest or missing lab values will be presumed confirmed:

1. ALT or AST > 8 x ULN, which is confirmed
2. ALT or AST > 5 x ULN, which is confirmed and persists for 2 weeks
3. ALT or AST > 3 x ULN (or the greater of 2 x baseline value or 3 x ULN if the baseline value was > ULN), which is confirmed and total bilirubin > 2 x ULN or INR > 1.5)

4. ALT or AST $> 3 \times$ ULN (or the greater of $2 \times$ baseline value or $3 \times$ ULN if the baseline value was $>$ ULN), which is confirmed, **and** with the new appearance (i.e., onset coincides with the changes in hepatic enzymes) of fatigue, nausea, vomiting, right upper quadrant pain or tenderness, fever, rash, and/or concomitant eosinophilia ($>$ ULN)

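### For patients whose baseline ALT/AST is above ULN, the protocol asks for a confirmatory retest at a higher level than those at which it acts on a confirmed value, so follow-up of an isolated elevation may not start

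*Combined protocol and SAP*

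**What the plan says.** Five parts of the protocol bear on a patient whose baseline ALT or AST is above ULN.

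- **Eligibility (Section 5.2).** Screening excludes "ALT or AST > 2xULN", so baselines above 1 and up to 2 x ULN are admitted.
- **Confirmation (Section 8.5.1, second paragraph).** At more than 3 x ULN, or at three times baseline where baseline was above ULN, "the initial measurement(s) should be confirmed as described above". In addition, "confirmatory measurements should also be performed if ALT or AST levels increase to" 5 x ULN.
- **Weekly retesting (Section 8.5.1, repeat measurements).** Patients with confirmed values above 3 x ULN, or at twice baseline where baseline was above ULN, "that are continuing to rise, they should have their liver chemistry tests" repeated at least weekly. The set is ALT, AST, INR and total bilirubin.
- **Work-up (Section 8.5.1, further investigation).** This applies to confirmed values above 3 x ULN or, where baseline was above ULN, above the larger of twice baseline and 3 x ULN.
- **Stopping (Section 8.6.1).** Rules 3 and 4 use the same level as the work-up: "the greater of 2 x baseline value or 3 x ULN if the baseline value was > ULN), which is confirmed". Rule 3 also needs raised bilirubin or INR. Rule 4 also needs new symptoms or eosinophilia. Rules 1 and 2 have no baseline adjustment: confirmed above 8 x ULN, and "ALT or AST > 5 x ULN, which is confirmed and persists for 2 weeks".

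Two general provisions apply as well. Section 8.5 requires confirmation of results that meet the monitoring criteria, and bars re-dosing after a value that reaches a stopping rule until the retest is back. Section 8.6.1 treats a value as confirmed when a retest was not done or is missing.

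**The concern.** Confirmation is the entry condition for weekly liver tests, for the work-up and for stopping rules 3 and 4. A retest trigger should therefore sit at or below the lowest level at which a confirmed value has consequences. For patients with a raised baseline it appears to sit above all of them.

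This is a patient-safety matter. Rules 3 and 4 are composites, so an ALT or AST elevation alone does not meet them. The weekly tests include bilirubin and INR, two of the markers that can complete rule 3. If those tests wait for a confirmation that Section 8.5.1 does not clearly request, a developing second component may be seen later than intended. Dosing is weekly (Section 6.1.3). From Day 36 the scheduled chemistry visits are 14 days apart (Appendix A; SAP Section 2.1.1, Table 4), so at least one further dose can fall due before the next scheduled panel. Sites could also handle the same result differently.

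**Working it through.** The plan gives no figure to reproduce; the check compares its own thresholds. Let b be baseline divided by ULN, with b above 1, and express every level in multiples of ULN. Three times baseline is taken to replace 3 x ULN when baseline is above ULN, and twice baseline likewise in the weekly-retest sentence.

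- Confirmation trigger (Section 8.5.1): min(3b, 5)
- Weekly-retest level (Section 8.5.1): 2b
- Work-up level, and ALT/AST component of rules 3 and 4 (Sections 8.5.1 and 8.6.1): max(2b, 3)

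| b | Confirm: min(3b, 5) | Weekly: 2b | Work-up/stop: max(2b, 3) | Confirm minus work-up/stop | Confirm minus weekly |
|---|---|---|---|---|---|
| 1.01 | 3.03 | 2.02 | 3.00 | 0.03 | 1.01 |
| 1.1 | 3.30 | 2.20 | 3.00 | 0.30 | 1.10 |
| 1.25 | 3.75 | 2.50 | 3.00 | 0.75 | 1.25 |
| 1.5 | 4.50 | 3.00 | 3.00 | 1.50 | 1.50 |
| 5/3 (1.67) | 5.00 | 3.33 | 3.33 | 1.67 | 1.67 |
| 2.0 | 5.00 | 4.00 | 4.00 | 1.00 | 1.00 |

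The gap to the work-up/stopping level has three pieces:

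1. For b from 1 to 1.5 it is 3b - 3, rising from 0 to 1.5.
2. For b from 1.5 to 5/3 it is 3b - 2b = b, rising to 1.67.
3. Above 5/3 the 5 x ULN trigger takes over and the gap is 5 - 2b. It falls to 1.0 at b = 2 and would close at b = 2.5, beyond the screening limit.

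Rules 1 and 2 have no gap. They start above 8 and above 5 x ULN, and min(3b, 5) never exceeds 5.

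Example: b = 1.5, ALT at 4.0 x ULN, bilirubin and INR normal, no symptoms. The value is above the work-up and weekly-retest levels (3.0 each) and above the ALT component of rules 3 and 4 (3.0). It is below the confirmation trigger (4.5). Neither rule is met, so the bar on re-dosing is not clearly engaged. Weekly tests and work-up both need a confirmed value, and the specific sentence on confirmation does not ask for the retest.

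**The case against.** The tempting stronger reading is that a stopping-level value may never be confirmed, so that dosing continues through a stopping event. The documents do not support that. Section 8.5 ties the retest to the stopping rule itself, independently of the trigger in Section 8.5.1, and bars the next dose until the result is back. If no retest is done, Section 8.6.1 presumes confirmation. For a patient who fully meets rule 3 or 4, these provisions work.

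A reader might also infer that the stopping rules in general are affected, or that events would drop out of the SAP's tables of confirmed elevations. Neither follows. Only rules 3 and 4 are touched. SAP Section 2.3.4 counts a value as confirmed when there is no retest within 7 days and uses cut-offs without baseline adjustment. Which values are retested can change whether one is downgraded, but an unretested value is counted, not lost.

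Two further arguments deserve weight. First, Section 8.5 says results meeting the monitoring criteria must be confirmed, and the lower levels in Section 8.5.1 could be counted among those criteria. That is arguable. However, those paragraphs take confirmed values as their starting point, and the one sentence that says when to confirm names a different level, so the general wording leads back to the disagreement. Second, *or* in the confirmation sentence might mean that either condition suffices. The trigger is then 3 x ULN for everyone, and the gap to the work-up/stopping level disappears. It is the less natural reading, since the reference to raised baselines would then do nothing. Even so, the weekly-retest level (2.2 x ULN at b = 1.1) stays below 3 x ULN for b under 1.5.

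The practical exposure is also limited. The scheduled chemistry panel includes bilirubin with ALT and AST, so a second component already present is seen at once, and panels continue every two weeks.

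**Conclusion.** The thresholds contradict one another for patients with baseline ALT or AST above ULN. On the natural reading, the confirmation trigger exceeds the work-up level and the ALT/AST component of rules 3 and 4 for every b above 1 and up to 2. The gap runs from near 0 to at most 1.67 x ULN.

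The surviving consequence is narrow. An isolated ALT or AST elevation inside the gap does not by itself meet rule 3 or 4. The provisions that protect a full stopping event are therefore not clearly engaged, and the weekly tests and work-up that could reveal the second component may not be started. This is a risk of delayed follow-up and of uneven practice between sites; it does not show that dosing would continue through a met stopping rule.

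The size rests on two assumptions: that three times baseline replaces 3 x ULN, and that baseline stays within the screening limit. Some comparison signs may have been lost in the text available, for instance before 5 x ULN; that would not change the comparison. The documents do not say how many patients have a raised baseline, so the number affected is unknown.

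**What to change.** Reconcile Sections 8.5, 8.5.1 and 8.6.1 so that every level at which the protocol acts on a confirmed ALT or AST value falls within the requirement to confirm. The clarification should say whether the baseline-based level replaces the ULN-based level or is an alternative to it, in each sentence where both appear. It should also say whether the presumption of confirmation in Section 8.6.1 extends to the weekly tests and work-up in Section 8.5.1. Which thresholds are right is for the sponsor's medical team.

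The cost is clarification or amendment wording and possibly a few extra retests. Sample size and analysis methods are unaffected.
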